1. BACKGROUND

This study will be conducted in partnership with a large funded randomized controlled trial, the **CO**coa **S**upplement and **M**ultivitamin **O**utcomes **S**tudy (COSMOS),^{1,2} and will examine the potential cognition-protecting effects of high-potency cocoa flavanol extract, with and without co-administration of a standard multivitamin (MTV) in adults 65 years and older, concurrently with their evaluation of cardiovascular disease (CVD) and cancer endpoints.

Cocoa Flavanol Effects on Cardiovascular Health

Cocoa, in its unprocessed form, contains high quantities of catechins and epicatechins, a subclass of flavonoids known as flavanols,^{3,4} and theobromine, an alkaloid of the cacao bean with vasodilation properties.⁵ Although the benefits of flavonoids have been studied for years, the health-promoting effects of cocoa flavanols caught the attention of the scientific community and public when low rates of hypertension and mortality due to CVD were reported in Kuna Indians living in the remote San Blas islands off the coast of Panama – protections that were lost with migration to urban areas. Extensive studies of the Kunas' lifestyle identified their dietary exposure to large amounts of cocoa flavanols as the primary contributing factor.⁶ Observational studies consistently demonstrate an inverse association between cocoa flavanol consumption and risk of CVD,⁷⁻¹⁰ and in clinical trials cocoa flavanols have robust favorable effects on cardiovascular health,¹¹⁻¹⁵ influencing endothelial function and flow-mediated dilation,^{16,17} blood pressure,¹⁸⁻²⁰ platelet adhesion and aggregation,^{21,22} lipid profiles,^{20,23,24} antioxidant capacity,^{20,25,26} systemic inflammation,²⁷ and insulin sensitivity and β -cell function.^{20,28,29} Pilot trials of up to 100 participants with 4-12 weeks of varying doses of cocoa flavanols in different patient groups provide consistent evidence for cardiovascular benefits at doses >700 mg/day and without adverse events.^{20,29-33} However, the benefits of cocoa flavanols on clinical CVD events in older adults have yet to be examined in a definitive trial.

Cocoa Flavanol Effects on Cognition and Brain Function

COSMOS-Mind will examine whether cocoa flavanols protect and even enhance cognitive function in older adults, an appropriate extension of the parent trial given the robust association between vascular and cognitive health.³⁴⁻³⁶ This association was the focus of a recent study of over 9,000 older adults drawn from the National Alzheimer's Coordinating Center: increased vascular risk, which included history of CVD and atrial fibrillation, predicted faster rates of cognitive decline in cognitively normal adults and in individuals with mild cognitive impairment (MCI).³⁶ Dietary consumption of cocoa flavanols may slow this decline through its beneficial effects on cerebral vasodilation, and thus on brain blood flow and perfusion, and angiogenesis.^{37,38} Epicatechin, the most common flavanol in cocoa, is rapidly absorbed, readily crosses the blood-brain barrier, can be detected in the brain,³⁹⁻⁴¹ and likely has accumulating physiological effects at high doses.^{40,42} This evidence for brain penetrance provides an important foundation for other cognition-enhancing mechanisms of flavanols at the neuronal level.^{43,44}

The effects of cocoa flavanols on cognition have been examined in animal studies for years, and consequently, putative underlying mechanisms related to endothelial function and pivotal signaling cascades for neuronal activity and viability are well described.³⁸ However, these mechanisms have not been fully explored in controlled clinical studies. Much of the support for a cognition-enhancing effect of flavanols in healthy older adults comes from observational studies, and a few small but promising controlled trials.^{45,46} In one large prospective study of 1640 older adults (≥ 65 yrs) followed for 10 years,⁴⁷ dietary intake of flavonoid-rich food (dark chocolate, wine, tea) was positively correlated with cognitive performance at baseline and over time in a dose-dependent manner. At the end of follow-up, participants in the lowest quartile for flavonoid

intake had lower Mini-Mental State Examination (MMSE) scores vs. those in the highest quartile. A favorable dose response of flavonoid intake on cognition was also reported in a large cross-sectional Norwegian study for a more extensive set of outcomes measuring attention and task-switching, verbal fluency, and spatial perception.⁴⁵ Regular flavonoid intake has also been linked to lower rates of prevalent cognitive impairment⁴⁸ and incident dementia.^{49,50}

Only a handful of controlled trials have examined the potential benefits of regular cocoa flavanol intake on cognitive function in older adults. While a few studies have failed to show cognitive benefits of cocoa flavanols,^{37,51-53} others provide compelling support to suggest that regular use of the high potency form of the extract may protect and possibly enhance cognitive function,^{20,54,55} a variability that likely reflects differences in methodology and/or extract formulation. In a small randomized, double-blind, 3-month trial of a high potency cocoa flavanol extract that is very similar to that administered in COSMOS, Brickman, et al. reported increased blood flow in the dentate gyrus and an associated improvement on a validated dentate gyrus-dependent memory task in older adults (50-69 years).⁵⁴ The strongest support for the proposed study is provided by the results of the Cocoa, Cognition, and Aging Study, a double-blind, 8-week randomized controlled trial of cocoa flavanols in 90 cognitively healthy older adults²⁰ and in 90 individuals with amnestic mild cognitive impairment (MCI)⁵⁵ at high risk for AD dementia. Participants consumed a daily drink with a high (993 mg) or medium (520 mg) dose, versus a low (45 mg) dose, of cocoa flavanols. Compliance exceeded 97% without adverse events. In both the healthy and MCI cohorts, performance on tests of attention and processing speed, task-switching and working memory, verbal fluency, and the global cognitive composite outcome improved for those in the high- and medium-dose groups relative to the low-dose group. In these participants, cocoa flavanols also lowered systolic and diastolic blood pressures, increased insulin sensitivity, and reduced a potent marker of oxidative stress. In both groups, a favorable treatment effect on insulin sensitivity was the primary determinant of cognitive response, consistent with a substantial body of work linking glucose regulation and cognitive function in older adults.⁵⁶⁻⁵⁹ This insulin sensitizing effect of cocoa flavanols, also reported by others,¹³ has important implications for older adults for whom the combined prevalence rate of type 2 diabetes and prediabetes exceeds 75% nationwide.⁶⁰ These findings demonstrate the potential efficacy of cocoa flavanol supplementation in the dose range proposed, and set the stage for this trial in cognitively healthy and mildly impaired older adults that will test whether regular intake of high dose cocoa flavanols can protect cognitive function and thus slow cognitive decline associated with normal and pathological aging, including AD. The extract's excellent tolerability profile provides added translational value.

Micronutrient Supplementation (Multivitamin) Effects on Cognition

COSMOS-Mind will also test whether daily use of a standard multivitamin benefits cognition in older adults. Although essential nutrient deficiencies in older adults have been associated with a higher risk of cognitive decline and dementia,⁶¹ the results of other studies examining MTV use for cognitive benefit remain controversial.⁶² Multivitamin use alone or with other therapies to enhance cognitive function in older adults has not been adequately examined in large randomized controlled trials (RCTs).⁶³ Controlled trials of a single nutrient focused on folic acid with or without other B vitamins,^{64,65} omega-3 fatty acids,^{66,67} and vitamin D^{61,68,69} have yielded mixed results, which could reflect the absence of a cognitive benefit or limitations in study design. Some of the design issues that contribute to this variability relate to the specific micronutrients administered and their interactions with one another, the cognitive tests selected, and variability in participant demographics and nutritional status.^{63,70} In the population-based Canadian Study of Health and Aging examining dementia onset in adults aged 65 years and older, participants reporting regular use of MTVs at baseline were less likely to experience significant cognitive decline during the 5-year follow-up.⁷¹ In a large RCT recruiting from multiple health care facilities in Scotland, daily use of a balanced multivitamin for 1 year improved verbal fluency, but only for those at least 75 years old or with a possible micronutrient deficiency at baseline (as per a risk questionnaire).⁷² The Physician's Health Study (N=5947, ≥65 years old) reported no effect of multivitamin use on cognition in older men.⁷³ These studies raise the possibility that micronutrient supplementation may only benefit cognitive function in adults who are vulnerable due to advanced age or poor nutrition. However, the effects of MTVs on cognition in older women have not been adequately examined in a large RCT.

2. OBJECTIVES

COSMOS-Mind is an ancillary cognitive study to the large randomized double-blind, placebo-controlled COSMOS trial, coordinated through Brigham and Women's Hospital (BWH). The parent trial will test whether high-potency cocoa extract supplement administered alone or in combination with a standard multivitamin reduce risks of CVD and cancer in older adults. COSMOS-Mind will test whether 3 years of treatment with these supplements improves cognitive function and reduces risk of cognitive impairment, including AD and other forms of dementia.

Primary Aim

- Test whether random assignment to daily cocoa extract (capsule containing 750 mg/d flavanols, including 75 mg (-)-epicatechin, and 90 mg theobromine), compared to placebo, has favorable effects on a composite measure of cognitive function, over 3 years of follow-up in men and women who are 65 years and older

Secondary Aims

- Examine the effects of MTV use over 3 years of follow-up, relative to placebo, on a composite measure of cognitive function
- Assess treatment effects on incident MCI, and AD and other related dementias
- Compare intervention effects on cognitive domains of executive function and episodic memory

Tertiary Aims

- Examine consistency of treatment response for subgroups defined by age, sex, body mass index, baseline cognitive status, CVD, and type 2 diabetes
- Examine treatment effects on measures of sleep quality, depressive symptoms, and subjective memory concerns
- Share COSMOS-Mind data with the parent trial and its ancillary studies to expand its scientific impact

3. DESCRIPTION OF PARENT TRIAL (COSMOS)

COSMOS is supported through an investigator-initiated award from Mars SymbioScience (PIs: Drs. [name] and [name] of BWH), and is a randomized, double-blind, placebo-controlled, 2x2 factorial clinical trial in 18,000 older women and men. The trial is testing a patented, well-studied cocoa extract supplement (capsules containing 750 mg/d flavanols, including 75 mg (-)-epicatechin, and 90 mg theobromine) and a daily MTV (Centrum Silver®, provided by Pfizer) in the prevention of CVD and cancer. COSMOS participants will be recruited from 2 large national cohorts of older adults (Women's Health Initiative Extension Study [observational; N=73,991]; VITamin D and OmegA-3 TriaL [eligible but unenrolled candidates; N=89,373]). The mean treatment and follow-up period in COSMOS will be 4 years. Participants will be asked to forego personal use of MTV and cocoa extract supplements while in the trial. Adherence and dietary intake of non-study supplements will be assessed via self-report using semi-annual questionnaires and pill count with nutrient biomarker measurements in a subset. A 3-month placebo run-in will eliminate those with poor compliance before randomization.

4. STUDY POPULATION

Inclusion and Exclusion Criteria

COSMOS-Mind will **include** 2500 participants from the parent trial who are at least 65 years of age, with approximately equal distribution of women and men.

The study will **exclude** participants with insulin-dependent diabetes. Insulin therapy, often associated with chronic hyperinsulinemia, can worsen cognition⁷⁴ and therefore potentially mask beneficial effects of the cocoa flavanols. COSMOS participants co-enrolled in the WHI Memory Study (WHIMS) will be excluded given their prior exposure to COSMOS-Mind cognitive tests. Also, participants who are unable to complete the baseline cognitive assessment will not be permitted to continue in the study. Adults with dementia will likely self-select out of enrollment in COSMOS-Mind, or be excluded given the demands of the placebo run-in period required for COSMOS. For the few with mild dementia who may enroll in COSMOS-Mind, randomization will ensure equal distribution by treatment assignment. Pre-enrollment cognitive assessments to identify dementia are not feasible for this large simple trial.

Recruitment and Consenting

Eligible COSMOS participants will be approached for enrollment in COSMOS-Mind and a second cognitive ancillary study (“COSMOS-Web”: involves a brief online computer assessment) using a single approach letter and recruitment flyer during the placebo run-in phase of the COSMOS trial. These materials provide information about COSMOS-Mind, expectations of participants, what is provided to participants, and how to enroll in the sub-study. Participants can choose to participate in one, both, or neither sub-study and will let the BWH Coordinating Center know of their decision by completing and returning a provided form. Consent to participate will be implied when participants indicate their willingness to participate in COSMOS-Mind on this form or by informing the COSMOS team by telephone or email. Implied consent will be used given the low participant burden and low risk associated with study participation as per Wake Forest School of Medicine IRB accepted practices.

Once enrolled, the COSMOS team at BWH will provide contact information and other parent trial outcomes for COSMOS-Mind participants to the Wake Forest COSMOS-Mind team using a secure web-based data transfer system. This seamless exchange of information between sites will permit timely accounting to ensure that the targeted demographics for enrollment are achieved (e.g. gender, age, race, ethnicity).

5. OUTCOMES

Face-to-face assessments of cognitive functioning are expensive in large multi-site studies and thus telephone-based protocols have been developed and validated. Telephone-based assessments have been used successfully in other studies and provide a valid and cost-effective method for tracking changes in cognitive status, including the development of MCI and dementia.

COSMOS-Mind will administer a telephone cognitive assessment to all participants annually by trained and certified staff of the Wake Forest COSMOS-Mind team. On the initial COSMOS-Mind call, consent to participate in the study will be confirmed and a brief hearing test will be administered to assess the participant's ability to successfully complete the interview. The interview will be 45 to 60 minutes in duration, and will include social time to support the relationship, and time to complete the hearing screening, cognitive tests, and questionnaires. The assessment battery consists of 6 validated tests and 3 validated questionnaires. A fourth validated questionnaire may be administered to a knowledgeable friend or family member (informant) identified by the participant if cognitive scores fall below pre-specified thresholds on a test of global cognition (i.e., TICSm) at any assessment.

A secure web-based call tracking system will be used to monitor participant contact, assessment dates, and attempts to complete interviews. Standard administration procedures of the telephone cognitive assessment will be for examiners to first record participants' responses on paper versions of the tests and then at a later time, enter the data into a dedicated and secure web-based database management system. As a quality assurance measure, each administration of the cognitive battery will be electronically audio-recorded to assist the examiner in scoring and to allow data quality assurance checks. Examiners will be trained and certified before administering their first assessment to a participant. Annual re-certification will be required.

Hearing Assessment

Before administration of the cognitive test battery, each participant will be asked a set of standardized questions: "Do you usually have trouble hearing when one person speaks to you?" "Do you usually have trouble hearing over the phone?" "Can you hear me well enough?" "Do you use a hearing device?" and "Is it in place?" and asked to repeat, "I have a cat so all I need is a dog." Based on the participant's responses, the examiner will adjust his/her test administration as needed. If hearing acuity is deemed significantly impaired, the examiner will terminate the assessment and the participant will not be permitted to continue in the study.

Cognitive Assessment

Telephone Interview for Cognitive Status-modified (TICSm) measures global cognitive function.⁷⁵ Fourteen items assess orientation, attention, language, learning and memory, psychomotor skills and abstraction. A modification to the original TICS added a second free recall trial to assess delayed memory for the 10-item word list.⁷⁶ In COSMOS-Mind, a third recall trial will be administered 15 minutes after this second recall trial, to quantify long delayed memory for the list. The TICSm has been previously validated for administration in older adults⁷⁵⁻⁷⁹ and used in large-scale epidemiological studies of cognitive impairment.⁸⁰ The TICSm correlates highly with other measures of global cognitive function, including the Mini-Mental State Exam ($r=0.86$), the Clinical Dementia Rating scale ($r=-0.75$), and with comparable cognitive tests administered face-to-face.^{79,81-83} The TICSm has excellent sensitivity (0.87) and specificity (0.89) to differentiate older persons with and without dementia⁸⁴ and to identify amnestic MCI,⁸⁵ and scores are normally distributed in population studies.⁸⁶

Immediate and Delayed Story Recall (SRI & II) measures verbal memory.⁸⁷ Participants are read a short story of 25 distinct elements, and are asked to recall as many elements as possible immediately after hearing the story (SRI) and again 15-20 minutes later (SRII). Alternate parallel forms of Story Recall will be administered from one annual assessment to the next, in counterbalanced order across participants, to minimize practice effects.

Oral Trail Making Test (OTMT)^{88,89} is a modified version of the original Trail-Making Test (TMT)⁹⁰ that measures attention (Part A) and executive function (Part B). The OTMT is highly correlated with the original TMT.⁹¹ For Part A, participants are asked to count from 1 to 25 as quickly as possible. For Part B, participants recite numbers and letters in an alternating fashion (1-A-2-B-3-C...13) as quickly as possible. Time to complete each task (seconds) is recorded.

Verbal Fluency is a measure of language accessibility and will be assessed using two tasks. *Category Fluency* requires participants to name as many exemplars of a semantic category as possible in 1 minute; two trials will be administered (categories = animals, vegetables). *Letter Fluency* requires participants to name as many words that begin with a specific letter of the alphabet in 1 minute; two trials will be administered (letters = F, L).⁹²

Number Span Test (NST)⁹³ measures simple attention and working memory (i.e., ability to manipulate transitory information in short-term memory). This task requires the participant to repeat a series of single-digit numbers of increasing span length, first in the same order as presented by the examiner (*Number Span Forward*) and subsequently in the reverse order (*Number Span Backward*). Number of correct responses is recorded.

Digit Ordering Test (DOT)⁹³ is a task of working memory. Participants are read a series of single numerical digits and are asked to recite the numbers in order from lowest to highest (e.g., '2-7-1' would be reordered as '1-2-7'). For each span length, 2 trials are administered. Span is increased by 1 number until participants are unable to successfully complete both trials of a given span length. Number of correct responses is recorded.

Additional Measures

Cognitive Change Index (CCI)⁹⁴ is a self-report questionnaire listing common experiences (e.g., “recalling conversations a few days later”, “remembering names and faces of new people”) and participants indicate amount of perceived change over a specified duration in the past (e.g., 5 years) using a Likert scale. To reduce participant burden, only the first 12 questions that address subjective memory concerns will be used to calculate the CCI score. The same 12-item subscale is used in the large multicenter Alzheimer’s Disease Neuroimaging Initiative-2 study.

Geriatric Depression Scale-Short Form (GDS-SF) measures depressive symptom severity,^{95,96} which is known to affect cognitive function. This 15-item (Yes/No) questionnaire can be administered orally, and has excellent psychometric properties and normative data.^{97,98} Participants who score >8 on this scale or whose general responses to examiners’ questions suggest significant emotional distress will also receive the supplemental Emotional Distress Test, which includes standardized questions about depressive severity and suicidal ideation. If a participant indicates any suicidal inclination, a study clinician experienced in the assessment and treatment of geriatric psychiatric disorders ([name]) will be informed, and will contact the participant to evaluate risk and make recommendations for follow-up.

Women’s Health Initiative Insomnia Rating Scale measures sleep disturbance and insomnia, which are known to impact cognitive function. This 5-item self-report questionnaire has excellent reliability and construct validity, and is sensitive to change over time.^{99,100}

Adjudication of Cognitive Status to Identify MCI, AD and Other Dementias

COSMOS-Mind will use the same procedures for ascertaining MCI and probable dementia (including AD) that were developed for WHIMS. All participants will be asked to identify a reliable informant at the time of the first telephone contact who could provide information about the participant’s cognitive and functional status. After each telephone cognitive assessment, suspected cases of cognitive impairment will be identified when TICSm<31, or, in follow-up Years 1-3 when the TICSm score drops by 0.5 of a standard deviation relative to age-appropriate normative data. For these participants, a trained interviewer will contact their informant to conduct a structured interview to complete the Dementia Questionnaire (DQ). This interview includes questions about current cognitive and behavioral functioning, and medical events and conditions that could impact cognition (e.g., stroke, psychiatric disorders).

In Years 4 and 5, after the planned follow-up annual evaluations are completed, all available test results and medical information for participants who triggered a DQ at any time during the study will be provided to 2 independent dementia experts. The information reviewed will include: cognitive data; self-report questionnaires about cognitive concerns, depression, sleep disturbances, and information on hospitalizations, medications and disabilities; informant responses on the DQ; and relevant health information available through the parent trial (including cardiovascular events and cancers). MCI classifications will include amnestic single domain, amnestic multi-domain, non-amnestic single domain, or non-amnestic multi-domain. If the adjudicator dyad agrees on the primary classification (MCI, probable dementia), no further discussion will occur; if the dyad disagrees, the case will be discussed by the entire adjudication panel until consensus is reached. Disagreements regarding MCI sub-classifications will be resolved within dyads and, if not possible, by the entire adjudication panel. For participants who receive a classification of ‘dementia,’ a letter will be sent to notify them that the test results indicated a possible cognitive impairment, and to encourage follow-up with a physician and further evaluation.

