Secondary and tertiary aims. COSMOS-Mind will assess the relative effects of assignment to MTV using parallel analyses to those described above. The study will also assess whether effects of the two treatments interact on the primary outcome, adding a term to the model used in the primary hypothesis. If so, results from the primary marginal comparisons will be qualified. Individual cognitive test scores will be analyzed – paralleling the strategy used to test the primary hypothesis – in supporting analyses. The randomization effects on tertiary outcomes including cognitive complaints, sleep quality, and depressive symptoms will be assessed similarly to the intervention models used in the primary and secondary aims, and further tests will determine whether the treatments interact with respect to tertiary outcomes. Linear contrasts will be used to estimate treatment effects at 3 years. Tests of interactions will also assess the potential moderating effect of treatments among subgroups formed by age (<70 or ≥70 years old), sex, BMI (<25, 25-29, ≥30 kg/m²), baseline cognitive function (median split on TICSm), cognitive complaints (median split on CCI), depressive symptoms (median split on GDS-SF), hypertension, and diabetes; additionally, the preceding variables will also be assessed as continuous moderators of the intervention effects. The distribution of follow-up times to MCI and dementia will be assessed with proportional hazards regression. COSMOS-Mind will incorporate CVD and cancer events (from the parent trial) as change-points in the primary analyses to assess their impact on post-event cognitive trajectories. When needed, transformations (e.g. Box-Cox, rank, probit) will be used to improve the symmetry of residual distributions.

Interim Testing

No interim monitoring of treatment effects on cognitive outcomes is planned. COSMOS-Mind investigators will remain masked to treatment assignment until the parent trial is completed. Routine reports will assess retention, data completeness and quality, and cognitive trajectories over time. These reports will be sent to the COSMOS Coordinating Center for inclusion in DSMB reports.

Statistical Power

Longitudinal sequences of cognitive test scores from the WHIMS-ECHO study (N=2,878; 1-6 years of annual telephone assessments) were used to calculate the longitudinal covariance of measures in a simulation analysis. Loss-to-follow-up was set to accumulate at 5% per year, as per rates observed in WHIMS.¹⁰⁴ Based

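### No rule identifies MCI already present at entry, so cases missed at baseline can later be counted as incident MCI

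*Protocol*

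**What the plan says.** The secondary aims (Protocol section 2) include: "Assess treatment effects on incident MCI, and AD and other related dementias". The analysis is one sentence in section 6: "The distribution of follow-up times to MCI and dementia will be assessed with proportional hazards regression".

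Ascertainment is in section 5, under adjudication of cognitive status. A TICSm below 31 at any assessment leads to the informant Dementia Questionnaire (DQ). A second route opens only after baseline: "or, in follow-up Years 1-3 when the TICSm score drops by 0.5 of a standard deviation relative to age-appropriate normative data". Experts review "participants who triggered a DQ at any time during the study", once, after follow-up has ended. Their output is a class: "If the adjudicator dyad agrees on the primary classification (MCI, probable dementia), no further discussion will occur". Section 8 adds an earlier look when DQ answers raise an alert, but it concerns dementia only and needs a DQ first.

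Section 4 does not exclude MCI, and the background describes the trial as one in healthy and mildly impaired people. The only provision for impairment at entry concerns dementia: "For the few with mild dementia who may enroll in COSMOS-Mind, randomization will ensure equal distribution by treatment assignment". The SAP does not mention MCI or dementia. Section 5 also states that "COSMOS-Mind will use the same procedures for ascertaining MCI and probable dementia (including AD) that were developed for WHIMS"; those procedures are not reproduced.

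**The concern.** An analysis of incident MCI needs a set of people free of MCI at the start and a rule for dating onset. Neither document gives one. A participant with MCI at entry who scores 31 or more has no baseline DQ and looks unimpaired in the record. Three further annual tests, each with measurement error, give three more chances to be flagged. Adjudicators then see evidence of MCI, and nothing asks them to say when it began.

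An analyst who takes the word incident seriously can remove cases detected at baseline, but not these. Randomization balances them between arms, which protects the test when treatment affects nobody. It does not make the hazard ratio an estimate of the effect on new cases.

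**Working it through.** **Inputs.** From the protocol: the cut of 31, the 0.5 SD drop, three follow-up visits, 2,500 participants and 5% loss per year. The documents give no MCI prevalence, incidence, hazard ratio (HR), event count or power; the power section covers the composite only. So there is no plan figure to reproduce, and every other input below is assumed.

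**1. How easily noise trips a follow-up trigger.** With retest correlation ρ and no true change, the difference of two scores has SD √(2(1−ρ)). At one visit, P(drop ≥ 0.5 SD) = Φ(−0.5/√(2(1−ρ))) = 0.288, 0.259, 0.215, 0.132 for ρ = 0.6, 0.7, 0.8, 0.9. For any of three visits sharing one baseline, simulation gives 0.515, 0.476, 0.411, 0.276. These are chances of an informant interview, not of an MCI classification. They use the raw score scale, not age norms.

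**2. Dilution.** Let f be the share of counted control-arm cases already present at entry, and k the active/control ratio of detection in those cases. Then approximately

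observed HR = (1 − f) × true HR + f × k.

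With true HR 0.75 and k = 1, f = 0.185 gives 0.815 × 0.75 + 0.185 = 0.796.

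**3. Simulation** (ρ = 0.8; MCI lowers TICSm by 1 SD; 31 is the lowest 10% of the cohort; true HR 0.75; existing MCI stable; perfect adjudication once triggered; all baseline-detected cases excluded). The baseline trigger misses 61% of baseline MCI, and 52% of those missed trip a follow-up trigger. Each cell shows f and the observed HR:

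| MCI incidence | 2% MCI at entry | 5% | 10% |
|---|---|---|---|
| 2%/yr | 12%; 0.775 | 25%; 0.815 | 42%; 0.863 |
| 3%/yr | 8%; 0.768 | 19%; 0.801 | 33%; 0.831 |
| 4%/yr | 6%; 0.769 | 15%; 0.792 | 27%; 0.812 |

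The Monte Carlo SE of each HR is about 0.005. With no baseline MCI counted, the HR is 0.746 to 0.758 throughout. A second model with heavier assumptions (5–20% MCI at entry, 1–3%/yr, mean TICSm 31–35 in MCI, error SD 2.5) gave f of 23–86% and HR 0.81–0.97.

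**4. Is the 0.5 SD trigger the cause?** Remove it from the first model, leaving only the cut of 31 at every visit. At 5% and 3%/yr, f goes from 19% to about 20% and the HR stays near 0.80–0.81, while events in 2,500 people fall from 190 to 93. In all nine cells f is equal or slightly higher without the trigger. In the second model f was lower with the trigger in 12 of 18 settings and slightly higher in 6.

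**5. Direction.** At f = 0.20: k = 1 gives 0.80; k = 0.75 gives 0.8 × 0.75 + 0.2 × 0.75 = 0.75; k = 0.60 gives 0.8 × 0.75 + 0.2 × 0.60 = 0.72. In the first model, with existing MCI declining 0.2 SD per year, the HR is 0.81 if treatment leaves that decline alone, 0.77 if it halves it and about 0.72–0.73 if it stops it.

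**6. Size against precision** (5%, 3%/yr, 2,500 participants). As written: 190 events, power 34%. With no baseline MCI counted: 150 events, power 41%. SE(log HR) ≈ 2/√190 = 0.145; the shift ln(0.80/0.75) = 0.065 is under half of that. Under the null, rejection was 4.4% as written and 5.1% with none counted (2,000 runs each).

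**The case against.** The tempting stronger reading is that the trial creates the problem by widening its trigger after baseline. The asymmetry is real, but step 4 does not support it as the cause. Repeating the cut of 31 with measurement error admits the same people, and the wider trigger finds true new cases about as readily. A drop from baseline also cannot exist at baseline.

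A second tempting reading is that the hazard ratio must move toward 1. That assumes treatment leaves detection unchanged in people already impaired. The protocol's own background reports better cognition with cocoa flavanols in an MCI cohort, so the opposite direction is open (step 5).

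Three further points have force. The aim says incident, and adjudicators see all available data, including the baseline tests and self-report, so they could recognise some cases; the simulation allows them none. The WHIMS procedures may contain a baseline rule that these documents do not show. And the consequence is small beside the sampling error of a secondary endpoint.

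What remains is that no text asks adjudicators for status at entry, or says what follows if they notice it.

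**Conclusion.** The point holds in limited form. Baseline ascertainment of MCI is incomplete and no rule removes or dates MCI present at entry, so the analysis of incident MCI can include it even after baseline-detected cases are excluded. If treatment does not alter detection in those people, a true hazard ratio of 0.75 would appear as roughly 0.77 to 0.86 over 2–10% MCI at entry and 2–4% incidence per year. Heavier assumptions take it closer to 1, and an effect on existing MCI could leave it unchanged or move it away from 1. The documents fix neither size nor direction. Type I error, under no effect on anyone, and the primary composite are not affected. Severity is minor, because power for this secondary endpoint is low either way.

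**What to change.** Before the Years 4–5 adjudication, add two items to the form for every adjudicated participant:

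- **Status at entry.** Masked adjudicators record it from the baseline battery and questionnaires, with the baseline DQ where one exists, before opening follow-up data.
- **Onset visit**, for each case classified as new.

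In the analysis, do not count baseline MCI or dementia as incident MCI, or baseline dementia as incident dementia. Baseline MCI stays at risk for dementia. Add a sensitivity analysis that defines the at-risk set for all participants by one prespecified rule on the SAP's baseline z-scores, so that exclusion cannot depend on who triggered later. If the WHIMS procedures already contain such a rule, reproduce it. Leave the primary analysis as it is. Removing or aligning the 0.5 SD trigger is not a remedy: it would lose true incident cases.

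The cost is wording and two form items, with no new data collection. The repair is partial. Participants with a baseline TICSm of 31 or more have no baseline DQ, so some cases at entry will be missed, and false positives will remove some true incident cases. With an assumed 70% sensitivity of the baseline review, the hazard ratio at 5% and 3%/yr moves from 0.80 to about 0.77, with 162 events instead of 190 and power of 39% instead of 34%. Allowing for imperfect specificity as well, it lands at about 0.76 to 0.78.
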